- Describe the study, providing detail regarding the study intervention (drug, device, physical procedures, manipulation of the subject or the subject’s environment, etc.). Discuss justifications for placebo control, discontinuation or delay of standard therapies, and washout periods if applicable. Identify procedures, tests and interventions performed exclusively for research purposes or more frequently than standard of care. Include alternative therapies, concurrent therapies discontinued per protocol, risk benefit ratio, and use of tissue/specimens. Discuss monitoring during washout periods if applicable. Include brief description of follow-up, if any.
- **Visit 1:** 0-3 months before benchmark clinic surveys on day of consent: approximately 30 minutes. Physical exam with Parkinson’s disease motor disability score as part of normal clinic visit that day. Participants will be randomized on a 1:1 basis to experimental vs control groups after consenting and prior to the start of this study visit. Subjects will complete the pre-clinic quality of life, treatment adherence, and self-efficacy surveys at this visit.
- **Visit 2:** Benchmark clinic from 8AM-1:30PM: Patients see social work, physical therapy, occupational therapy, speech therapy, and pharmacy in a scheduled rotation for about 45 minutes each. Social work and pharmacy visits may be done earlier in the week depending on provider and patient availability. After these evaluations, the team meets with the physician movement disorders specialist for a team discussion of care needs. Following this meeting, the physician meets with the patient to summarize the results and discuss ongoing needs and action items and enter appropriate referrals and orders. The benchmark day lasts from around 8AM-1:30 PM with a built in 45 minutes for lunch from 12:15-1PM.

- **Visit 3:** 3-6 months Follow up study point surveys: approximately 30 minutes. The control group will not participate in the benchmark clinic (Visit 2) and instead, their physician movement disorders specialist will make allied health referrals as part standard clinical care during a physician visit on the same day as study visit 2. They will still complete visit 3.

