Power calculations were performed using the published mean and SD for the self-efficacy scale. 73 participants per arm (control/experimental) for a total of 146 participants provides an 80% power to detect a 1 point change, which is felt to be a minimal clinically relevant change. We plan to recruit 100 participants per arm to account for any dropout. The maximum possible capacity of our benchmark clinic is 250 people per year for logistical/scheduling reasons so our sample size was chosen as a realistic number given our power calculation, total capacity, and expected interest of participants.

Secondary outcomes include change in total weekly minutes exercised, change in "engagement score" from the patient engagement survey (Likert scale 1-5 choices converted to 0, 25, 50, 75, and 100 to calculate composite engagement score as a mean of all Likert scale items), and change in Zarit (caregiver burden score). We will also compare total amount of skilled therapy visits, hospitalizations and ER visits, falls, and number of contraindicated medication combinations between the groups. All of these analyses will also be done using repeated measures ANOVA.

Subgroup analyses for the above outcomes will be performed using MOCA as a measure of baseline cognitive status and MDS-UPDRS as a measure of baseline disease severity both performed as linear regressions.

All enrolled subjects who complete the study visits will be included for analysis. Eligibility requirements are minimal (only need a diagnosis of Parkinson's disease) and those who do not have a diagnosis of Parkinson's disease will not be approached for this study, so we do not anticipate a significant number of ineligible

participants/screen failures. If for an unforeseen reason a participant is felt to not have a diagnosis of Parkinson's disease by a movement disorders specialist after enrollment, they will be removed from the study.

Estimated time to target accrual is 1 year with an accrual rate of 9 participants per arm per month.

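### Falls, hospital/ER visits and therapy visits are compared as raw totals with no counting window, look-back or term for observation time, and equal windows in the two arms are not secured

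*Combined protocol and SAP*

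**What the plan says.** The secondary-outcome paragraph of Data Analysis & Statistical Considerations lists several outcomes as changes, for example "change in Zarit (caregiver burden score". It then adds: "We will also compare total amount of skilled therapy visits, hospitalizations and ER visits, falls, and number of contraindicated medication combinations between the groups". The method is one sentence: "All of these analyses will also be done using repeated measures ANOVA". No counting period, look-back, rate or offset is given. The closing paragraph on data storage says that medical records will be queried for health-care use, without dates.

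The visit timing comes from Design & Procedures:

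- Randomisation: "Participants will be randomized on a 1:1 basis to experimental vs control groups after consenting and prior to the start of this study visit".
- Visit 1: "0-3 months before benchmark clinic surveys on day of consent: approximately 30 minutes".
- Visit 3: "3-6 months Follow up study point surveys: approximately 30 minutes". The visit from which this is counted is not named.
- Control physician visit: the text under Visit 3 puts it on the day of Visit 2. The paragraph that follows puts it on the day of Visit 1. Both are current text.

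Subject Recruitment and Compensation ties payment to completion of Visit 2, described as either the benchmark or the standard visit. The analysis set is defined as follows: "All enrolled subjects who complete the study visits will be included for analysis".

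**The concern.** A total has meaning only with the period over which it was counted. Here that period can vary two-fold between participants (3-6 months), or three-fold if counting starts at Visit 1 and Visit 3 is set from Visit 2 (3-9 months). Variation shared by both arms only adds noise. Variation that differs by arm makes a difference in follow-up look like a difference in event rate, and the conflict over the control visit leaves that possible.

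Repeated-measures ANOVA also needs a count at two times. The plan does not say whether a pre-study count exists or how long a period it covers. For therapy visits, it does not say whether the physical, occupational and speech therapy evaluations on the benchmark day are included.

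Falls and hospital/ER use are clinical outcomes named in the study objective. Contraindicated medication combinations can be counted at a point in time, so they are not affected.

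**Working it through.** **Inputs.** From the documents: Visit 1 is 0-3 months before the clinic; Visit 3 is at 3-6 months; 73 participants per arm (power calculation) and 100 per arm (recruitment). The plan's power figure concerns the self-efficacy scale, so there is no stated figure for the counts to reproduce. Assumed: visit times uniform within their ranges; gamma-Poisson counts in six settings of (events per month, dispersion): (0.25, 2), (0.5, 1), (0.5, 2), (0.5, 4), (1, 2) and (0.05, 2); two-sided 5% tests. Totals are compared by t-test. With two time points, the arm-by-time test equals a t-test on follow-up minus look-back count.

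**Windows.** Let G be the Visit 1 to clinic gap, uniform on 0 to g months, and F the 3-6 month interval (mean 4.5).

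| Counting starts at | Visit 3 and control timing | Experimental window | Control window |
|---|---|---|---|
| Visit 1 | Visit 3 anchored the same way in both arms | equal | equal |
| Visit 1 | Visit 3 set from Visit 2 in the experimental arm, from Visit 1 in controls | G + F | F |
| Clinic or referral visit | Controls referred at Visit 1, common Visit 3 timetable | F | G + F |

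With no treatment effect, the longer-window arm has an expected total (g/2 + 4.5)/4.5 times the other:

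- g = 1: 5.0/4.5 = 1.11
- g = 2: 5.5/4.5 = 1.22
- g = 3: 6.0/4.5 = 1.33

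**False positives on totals, unequal windows** (second row, no effect, 10,000 trials per setting, range over the six settings):

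| Gap (months) | 73 per arm | 100 per arm |
|---|---|---|
| 0-1 | 5.4-8.2% | 5.6-9.0% |
| 0-2 | 7.1-16.2% | 8.7-20.8% |
| 0-3 | 10.0-28.4% | 12.6-37.4% |

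A repeat for the 0-3 month gap gave 10.4-29.3% and 12.9-38.4%, hence about 10-38%. The third row of the window table is the mirror image of the second, so the rates are the same and the direction reverses. Simulated directly at 0.5 events per month, 73 per arm and a 0-3 month gap, the third row gave 27.8% at dispersion 1 and 17.8% at dispersion 2, against 28.4% and 17.8% for the second. Negative binomial regression with a log-time offset gave 4.4-6.4% (0-1 and 0-3 month gaps, second row).

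**Shared window.** False positives on totals are 4.2-5.7%. At a rate ratio of 0.6, the offset changes size-adjusted power by -0.2 to +4.1 points (median about 2). For example, at (0.5, 2) with 100 per arm it goes from 57.1% to 60.2%.

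**If baseline counts are used.** At a constant 0.5 events per month, a 3-month look-back expects 0.5 × 3 = 1.5 events and a 4.5-month follow-up expects 0.5 × 4.5 = 2.25. The raw change is +0.75, a 1.5-fold rise with no change in rate. Size-adjusted power at (0.5, 2), 100 per arm, rate ratio 0.6, follow-up 3-6 months:

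| Look-back and stability of each person's rate | Totals | Change (ANOVA) | Negative binomial, offset + baseline |
|---|---|---|---|
| 3 months, stable | 55.4% | 89.3% | 86.1% |
| 6 months, stable | 57.1% | 56.4% | 94.3% |
| 6 months, correlation 0.5 | 56.5% | 31.2% | 59.6% |

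The change test can therefore gain or lose power against totals. The negative binomial model with a baseline count is not always best. At dispersion 4 with correlation 0.5, its likelihood-ratio test runs at 9.1-9.6% under no effect, and its robust test at 7.2-8.7%.

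**Dilution from counting at randomisation.** For a post-clinic rate ratio of 0.60:

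- 0-1 month gap: (0.5 × 1 + 4.5 × 0.6)/5.0 = 0.64
- 0-3 month gap: (1.5 × 1 + 4.5 × 0.6)/6.0 = 0.70

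**The case against.** The strongest reply is that the arms are randomised and probably share a timetable. The payment text treats Visit 2 as existing in both arms, and one of the two control paragraphs agrees. On that reading the planned comparison is valid and the missing offset costs about 2 power points. The plan also speaks of change for some outcomes but of totals between groups for these, so baseline counts may not be intended, and the look-back results would then not apply. The count model has its own problem with test size once a baseline count is added.

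All of this stands, and it limits the point. It does not supply a window or remove the contradiction over the control visit. Nor does it explain how a repeated-measures analysis is run on a single total. The survey list at Visit 1 ("Subjects will complete the pre-clinic quality of life, treatment adherence, and self-efficacy surveys at this visit") does not settle whether baseline counts exist, since it also omits the Zarit score, whose change is analysed.

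A reader might also infer that the benchmark-day therapy evaluations should simply be excluded. If counted, they add three visits per experimental participant by design. But controls receive allied health referrals, and their first evaluations would still count. Excluding evaluations in one arm only can bias against the clinic.

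**Conclusion.** The point holds as a gap that should be closed before analysis. The plan fixes neither the period over which events are counted nor its equality between arms.

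A reader might infer that the planned tests have inflated error, or that they favour the benchmark clinic. The documents support neither. Inflation requires windows that differ by arm, which takes a particular combination of control timing, Visit 3 anchor and counting origin that the text leaves open but does not prescribe. Two such combinations lengthen opposite arms, so even the direction is undetermined. Nor do the documents show that the ANOVA wastes power: with a short look-back and stable rates, it does far better than totals.

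The size is therefore conditional: about 2 power points with a shared window, and about 10-38% false positives with unequal windows and a 0-3 month gap. If baseline counts are used, raw change cannot be interpreted unless look-back and follow-up lengths match or are adjusted for. Every event rate, dispersion and timing distribution is assumed. All affected outcomes are secondary and no power is claimed for them. Confidence is medium.

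**What to change.** 1. Reconcile the two control-visit paragraphs in Design & Procedures.
2. Count events in both arms over one dated window, from randomisation at Visit 1 to Visit 3, with Visit 3 anchored the same way in both arms.
3. Analyse falls and hospitalisations/ER visits, and therapy visits if rates are wanted, by negative binomial regression with arm and log(days observed) as offset. Report rate ratios.
4. Add a baseline count as covariate only where it is available in both arms over one fixed look-back. Use a robust or re-randomisation test with it; at high dispersion the robust test alone may still exceed 5%.
5. Report therapy visits with and without the benchmark-day physical, occupational and speech therapy evaluations, and state the asymmetry.
6. If participants who miss Visit 2 are to be kept for these outcomes, change the completer rule as well. Moving the start of counting does not do this.

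The cost is mostly wording, plus recording the randomisation and Visit 3 dates. Results become rate ratios rather than mean differences, and counting from randomisation includes time before the clinic, with the dilution shown above. If both arms already share one window and no baseline counts exist, the gain in power is only about 2 points.

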The control group will not participate in the benchmark clinic (Visit 2) and instead, their physician movement disorders specialist will make allied health referrals as part standard clinical care during a physician visit on the same day as study visit 1. They will still complete visit 3.

Selection of Subjects

- List inclusion/exclusion criteria and how subjects will be identified.

Subjects will be from the patient population with Parkinson's Disease over the age of 30. Caregivers will be required for participation. All subjects must be able to provide consent. Subjects will be contacted first with the phone script by a study email address.

Subject Recruitment and Compensation

- Describe recruitment procedures, including who will introduce the study to potential subjects. Describe how you will ensure that subject selection is equitable and all relevant demographic groups have access to study participation (per 45 CFR 46.111(a) (3)). Include information about approximately how many DUHS subjects will be recruited. If subjects are to be compensated, provide specific prorated amounts to be provided for expenses such as travel and/or lost wages, and/or for inducement to participate.

This study will be discussed with Parkinson's Disease patients when considering referring them to our already established benchmark clinic. All patients already scheduled for an upcoming benchmark clinic will be called or emailed to see if they would like to enroll.

Patients who are randomized to standard care will have the opportunity to participate in the benchmark clinic within 1 year but not as part of this study. 200 subjects will be enrolled (100 benchmark clinic and 100 controls for standard of care). Payment of the subject will be upon completion of visit 2 (the benchmark visit or standard visit)

Subject's Capacity to Give Legally Effective Consent

- If subjects who do not have the capacity to give legally effective consent are included, describe how diminished capacity will be assessed. Will a periodic reassessment occur? If so, when? Will the subject be consented if the decisional capacity improves?

Subjects with diminished capacity will not be consented.

Study Interventions

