RedCap and Duke Box will be used for data storage. A key will be used to link unique identifiers to participants responses. The key will be used to track completion of longitudinal data, as well as to query Duke Health medical records for health utilization (e.g. ED visits) as a secondary study outcome. The file connecting Study ID with Duke MRN will be encrypted and stored on the Duke Movement Disorders secure folder on the neurology private drive and will be password-protected. Only the study investigators will have access to this file.

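### The only analysis set is participants who complete the study visits; in the experimental arm Visit 2 is the intervention itself, and there is no intention-to-treat set or missing-data plan

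*Combined protocol and SAP*

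**What the plan says.** **Analysis set.** Data Analysis & Statistical Considerations gives one rule: "All enrolled subjects who complete the study visits will be included for analysis". It does not define completion. No other analysis set, missing-data method or sensitivity analysis appears in the document.

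**Order of events.** Design & Procedures, Visit 1: "Participants will be randomized on a 1:1 basis to experimental vs control groups after consenting and prior to the start of this study visit". All three visits therefore follow randomisation.

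**Visit 2 by arm.** In the experimental arm Visit 2 is the benchmark clinic, from 8AM to 1:30PM. Controls do not attend it; a physician makes their referrals at a routine visit. The Visit 3 item of Design & Procedures puts that visit "during a physician visit on the same day as study visit 2". The paragraph that closes the same section puts it "during a physician visit on the same day as study visit 1". The payment text under Subject Recruitment and Compensation assumes that both arms have a Visit 2.

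**Record-based outcomes.** The closing paragraph on data storage says the linking key will be used to query "medical records for health utilization (e.g. ED visits) as a secondary study outcome".

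**Dropout and re-diagnosis.** Dropout is handled only through recruitment: "We plan to recruit 100 participants per arm to account for any dropout". For a participant whose diagnosis is later revised, the text ends: "by a movement disorders specialist after enrollment, they will be removed from the study".

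**The concern.** Completing the visits happens after randomisation, and what it requires depends on the arm. An experimental participant must attend a half-day clinic, which is the care model being tested. A control needs a physician visit at most and, on one of the two descriptions, has no separate Visit 2. Restricting the analysis to completers can therefore remove different kinds of people from the two arms.

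The link to the outcome is plausible. The primary outcome is change in self-efficacy, which the objectives present as engagement with self-care, and the background says travel and scheduling keep patients from care. Attending a long clinic day may well be related to that outcome. If non-attenders would have changed differently from attenders, the estimated effect is biased. The direction is open: non-attenders may have less capacity to improve or more room to improve, and controls may drop out more. Either a positive or a null result would be harder to attribute to the clinic.

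The same sentence, taken as written, also drops non-completers from utilisation outcomes that come from medical records and need no study visit.

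**Working it through.** **1. The plan's own figure.** The sample size is 73 per arm for 80% power to detect 1 point. SD, alpha and sidedness are not stated, so the figure can only be solved backwards. With two-sided alpha 0.05 and the normal approximation:

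SD = 1 / [√(2/73) × (1.960 + 0.842)] = 1 / (0.1655 × 2.802) ≈ 2.16.

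The t-test version gives 2.14; one-sided 0.05 would give 2.43. I use 2.14 as the SD of change. This is an assumption, not a reproduction.

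**2. Headroom.** Enrolling 100 against 73 needed allows 1 − 73/100 = 27% loss per arm. That is the maximum loss that preserves planned power, not a stated dropout rate. It protects power and does nothing about bias.

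**3. Illustration A: the avoidable part.** Assumptions: no true effect, 100 per arm, 10% random loss at Visit 3 in both arms. A share *f* of the experimental arm misses Visit 2 but is as reachable at Visit 3 as anyone else. Attenders and non-attenders differ by *g* in mean change. The attenders' mean exceeds the whole-arm mean by *f × g*, so:

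bias of completer analysis = *f × g*.

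Check by hand for *f* = 10%, *g* = 1. The analysed numbers are 81 and 90. SE = 2.14 × √(1/81 + 1/90) ≈ 0.328. Bias/SE = 0.10/0.328 ≈ 0.305. Type I error ≈ P(Z > 1.655) + P(Z < −2.265) ≈ 0.049 + 0.012 = 0.061.

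Simulation, 20,000 trials per row:

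| *f* | Bias, *g* = ±1 point | Type I error, completers | As randomised |
|---|---|---|---|
| 5% | ±0.05 | about 5% | bias 0, 5% |
| 10% | ±0.10 | 6% | bias 0, 5% |
| 20% | ±0.20 | 9% | bias 0, 5% |

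**4. Illustration B: overall loss related to the outcome.** Completion odds are multiplied by e^0.5 to e^1 per SD of change; no true effect; 100 per arm; 20,000 trials per setting.

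| Loss, experimental / control | Selective arms | Bias (points) | Type I error |
|---|---|---|---|
| 27% / 10% | both | 0.17 to 0.29 | 8% to 15% |
| 27% / 10% | experimental only | 0.27 to 0.49 | 13% to 32% |
| 20% / 10% | both | 0.10 to 0.17 | 6% to 9% |
| 27% / 27% | both | about 0 | 5% |
| 10% / 27% | both | −0.17 to −0.30 | 8% to 15% |

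Here an as-randomised analysis recovers only the people who can be reached at Visit 3, so B shows the exposure and not what the fix would remove.

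**5. Cost in power of analysing as randomised.** If a share *q* of the experimental arm does not attend and gains nothing, a 1-point effect becomes 1 − *q*.

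| *q* | Effect | Power, 90 per arm | Power, 100 per arm | n per arm for 80% power |
|---|---|---|---|---|
| 10% | 0.9 | 80% | 84% | 73/0.81 ≈ 90 |
| 20% | 0.8 | 70% | 75% | 73/0.64 ≈ 114 |

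**The case against.** The sentence says who is included; it does not say that everyone else is excluded. Completion could mean the two survey visits common to both arms, Visits 1 and 3. On that reading missing the clinic day excludes nobody, and only ordinary Visit 3 attrition remains. In addition, one description of the control arm and the payment text give controls a visit at the same time point, so both arms could lose people there. Candidates are partly those already booked for the clinic, and payment depends on Visit 2, so non-attendance may be low; controls who lose a booked place might drop out more. At 5% or 10% non-attendance, Illustration A shows little inflation of the type I error. The large figures come from Illustration B, which the fix would only partly remedy. The data-storage paragraph does not limit the record query to completers.

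Much of this is fair and limits the claim about size. It does not remove the defect. The section's template asks which subjects will be analysed, and this sentence is the only answer. If the narrower reading is intended, the plan has to say so. Even where controls have a same-day visit, a physician appointment is a different hurdle from a half-day clinic. On every reading there is no intention-to-treat set and no method for missing Visit 3 scores.

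**Conclusion.** The concern holds and should be fixed. The plan states a completer rule that depends on an event after randomisation, which for the experimental arm includes receiving the intervention. It offers no as-randomised analysis and no missing-data plan. The rule governs the primary comparison and, as written, every secondary one.

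The size of any bias cannot be derived from the documents. Under the Illustration A assumptions (SD 2.14, two-sided 0.05, a 1-point difference between attenders and non-attenders), the avoidable bias is 0.05 to 0.20 point for 5% to 20% non-attendance, against a 1-point target, with type I error of about 5% to 9%. The direction is unknown. The case rests on the missing analysis principle and the low cost of supplying it, not on the larger figures in Illustration B. Removal after re-diagnosis is a minor further instance; the plan expects few.

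**What to change.** Replace the sentence on who is analysed with:

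> The primary analysis includes all randomised participants in their assigned arm, whether or not they attended Visit 2.

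Then:

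- Seek Visit 3 surveys from everyone, including those who missed Visit 2. Surveys never sought may not be recoverable later.
- Take record-based utilisation outcomes for all randomised participants.
- Fit a likelihood-based mixed model to all available data (multiple imputation would also serve), with a sensitivity analysis for missing Visit 3 data.
- Keep the completer analysis as supportive only, with completion defined for each arm.
- Reconcile the two statements on the day of the control physician visit, because they decide what completion means for controls.
- Minor: keep re-diagnosed participants in the primary set and exclude them only in a sensitivity analysis.

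The cost is SAP wording and survey contact with people who missed the clinic; the change itself calls for no extra patients. The estimate may be diluted by non-attenders. If 10% of the experimental arm do not attend and gain nothing, power stays at about 80% (90 per arm analysed) to 84% (100 per arm). At 20% it falls to about 70% to 75%, and holding 80% would take about 114 per arm, so attendance should be monitored.

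### Removing participants whose Parkinson's diagnosis is revised after enrolment is a post-randomisation exclusion that could differ by arm; the bias is probably small, in an unknown direction, and cheap to prevent

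*Combined protocol and SAP*

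**What the plan says.** The removal rule is in the combined protocol and SAP, under Data Analysis & Statistical Considerations. If it emerges that a participant is thought not to have Parkinson's disease "by a movement disorders specialist after enrollment, they will be removed from the study". The text sets no diagnostic criteria and no time limit. It does not say which specialist decides, or on what information. The same paragraph treats such cases as unforeseen and expects few ineligible participants.

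The timing of randomisation is in Design & Procedures, Visit 1: "Participants will be randomized on a 1:1 basis to experimental vs control groups after consenting and prior to the start of this study visit".

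Contact after randomisation differs by arm. For the clinic arm, Visit 2 states: "Patients see social work, physical therapy, occupational therapy, speech therapy, and pharmacy in a scheduled rotation for about 45 minutes each". Then "the team meets with the physician movement disorders specialist for a team discussion of care needs", and a physician meets the patient. For the control arm, a movement disorders specialist makes allied health referrals. The Visit 3 paragraph places this "during a physician visit on the same day as study visit 2", while the closing paragraph of the same section places it "during a physician visit on the same day as study visit 1".

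**The concern.** Randomisation makes the arms comparable as they stand at allocation. A rule that later drops people, on information that may depend on the arm, can undo part of that. Three features make this possible here:

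- Almost every specialist contact in the study, including the Visit 1 motor examination, comes after allocation.
- The rule has no safeguard: no arm-unaware decision, and no restriction to what was known before allocation.
- The clinic intervention itself produces extra clinical information and passes it to a specialist.

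If those removed would have changed differently on self-efficacy from those kept, and if removal is more common in one arm, the between-arm difference in mean change is shifted by something other than the treatment. The secondary outcomes would be exposed in the same way.

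This is distinct from the neighbouring sentence that limits the analysis to people who complete the study visits. That sentence drops people who miss visits; this rule drops people who would have attended all of them. Repairing one leaves the other in force.

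**Working it through.** **1. Order of events.** Consent, then randomisation, then Visit 1, then Visit 2 or the control physician visit, then Visit 3. Removal can occur at any point after enrolment. A removal prompted by anything seen at Visit 1 or later is therefore a post-randomisation exclusion.

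**2. Opportunity by arm.**

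| Source of information for the specialist | Clinic arm | Control arm |
|---|---|---|
| Visit 1 examination with motor score | Yes | Yes |
| Five evaluations of about 45 min (5 × 45 = 225 min) | Yes | Not as a study visit; referrals are made |
| Team discussion with the specialist | Yes | No |
| Physician visit after allocation | Yes, at Visit 2 | Yes; day of Visit 1 or of Visit 2, depending on the paragraph |

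The arms differ clearly in the information assembled for the specialist. They differ less clearly in specialist contact itself.

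**3. The plan's own figure.** The plan gives 73 per arm for 80% power to detect 1 point, with 100 per arm recruited. The SD, alpha and sidedness are not stated, so 73 cannot be reproduced independently. The SD can be back-solved by assuming a two-sided alpha of 0.05 and a comparison of two means:

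SD = 1 / [(1.960 + 0.842) × √(2/73)] = 2.16 (normal approximation); the t-test version gives 2.14.

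I use 2.15, which returns 73 per arm. A one-sided 0.05 would imply about 2.43. The sample size is not in dispute; the SD is needed only for scale.

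**4. Formula.** Let p be the proportion removed in an arm and D the mean change in those retained minus that in those removed. Removal shifts the arm's mean change by p × D. Hence

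bias = p(clinic) × D(clinic) − p(control) × D(control).

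Bias is zero if p and D are the same in both arms. The documents give neither p nor D. All values below are assumptions, with D taken as equal in both arms. D may have either sign, so the results are sizes, not directions.

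**5. Results.**

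| Removed, clinic v control (assumed) | D (assumed) | Calculation | Bias, points |
|---|---|---|---|
| 2% v 0% | 1 SD = 2.15 | 0.02 × 2.15 | 0.04 |
| 6% v 2% | 2 points | 0.12 − 0.04 | 0.08 |
| 10% v 2% | 2 points | 0.20 − 0.04 | 0.16 |
| 10% v 0% (extreme) | 1 SD = 2.15 | 0.10 × 2.15 | 0.22 |

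With SD 2.43 the first row becomes 0.02 × 2.43 = 0.05.

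**6. Effect on the test.** With 100 per arm, the standard error is 2.15 × √(2/100) = 0.304. Shifting a two-sided 5% normal test by the bias gives a type I error of 5.2% in the first row and 10.9% in the extreme row.

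**The case against.** The strongest objection is that only a movement disorders specialist's judgement triggers removal, and both arms see one. Therapists, social workers and pharmacists cannot remove anyone. Both arms have the Visit 1 examination, and controls also have a physician visit. If that visit falls on the day of Visit 2, the arms have the same number of specialist-contact days. Controls are referred to allied health as well. Recruitment is from known Parkinson's patients who are being considered for, or are already scheduled for, the clinic, so few revised diagnoses are likely.

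Much of this stands. It rules out several stronger readings that a reader might infer:

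- **That clinic participants will be removed more often.** The documents support only that they could be, because the team discussion passes information to the specialist that a control visit may lack. The two statements of the control visit's timing must be reconciled before the contrast can be judged.
- **That the bias favours the clinic, because atypical or poorly responding patients would leave that arm.** Nothing in the documents says who would be re-diagnosed or how they would score.
- **That the deciding specialist runs the intervention and knows the arm.** This is likely, since no blinding is described, but the rule does not identify the specialist.
- **That removal ends data collection for good.** This is a natural reading, but the documents do not say what happens to the data of removed participants.

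The objection does not dispose of the rule itself. It is still a post-randomisation exclusion without safeguards. If cases are as rare as expected, keeping them costs almost nothing.

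**Conclusion.** The point holds as a weakness worth correcting, not as evidence of serious bias. The timing and the missing safeguards come directly from the documents. That removals could differ by arm is a reasonable inference from the design; the amount and the direction are unknown.

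A few cases in one arm only, such as 2 of 100, would shift the comparison by about 4% of the 1-point target and hardly affect the type I error. Reaching 8% to 16% of the target requires 6 to 10 removals per 100 in the clinic arm against 2 in control, and a 2-point difference between those kept and those removed. That is more removals than the plan's expectation of few cases suggests. All these sizes rest on assumed removal rates, an assumed D and, where D is in SD units, a back-solved SD.

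A reader might conclude that randomisation no longer protects the comparison. At these sizes that is too strong. The completer-only analysis set in the same section is probably the larger source of post-randomisation exclusion.

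**What to change.** 1. In Data Analysis & Statistical Considerations, replace the removal sentence with: *A participant whose diagnosis is revised after randomisation stays in follow-up, completes Visit 3 and is analysed in the assigned arm; the revision and its date are recorded and reported by arm.* With these participants kept, the bias from this rule is zero by construction, and 73 and 100 per arm are unchanged.
2. Check the diagnosis from existing clinic records before randomisation. Using existing records lets the Visit 1 timing of randomisation stand; requiring a new specialist examination first would conflict with it.
3. Add a sensitivity analysis that excludes participants with a revised diagnosis, labelled as a post-randomisation exclusion. An arm-unaware reviewer would strengthen it, but may need extra staff and is not essential.
4. Reconcile the two statements in Design & Procedures about the day of the control physician visit.

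**Cost:** protocol wording, a records check for each participant and one additional analysis. The downside is that a few participants without Parkinson's disease may stay in the primary analysis and slightly dilute the effect.
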